2.3.2 Secondary Endpoints

- Time to PSA progression with 1st line AAT + 2nd line AAT (TTPP2)
- PSA response rate to 1st line AAT (decrease by at least 50% or 90% from baseline)
- PSA response rate to 1st line AAT at Week 13 (decrease by at least 50% or 90% from baseline)
- Time to PSA decrease by 50% from baseline with 1st line AAT
- Time to treatment failure of 1st line AAT (TTF1)
- Time to treatment failure of 2nd line AAT (TTF2)
- rPFS

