3.1.4 Exploratory Objectives

- To evaluate time to PSA progression with 2nd line AAT (2nd time to PSA progression [2nd TTPP]).
- To evaluate PSA response rate to 2nd line AAT.
- To determine the benefit of enzalutamide + ADT therapy as compared to flutamide + ADT therapy as assessed by metastasis-free survival (MFS).

To evaluate Quality of Life (QOL) on 1st line AAT and 2nd line AAT using Functional Assessment of Cancer Therapy—Prostate (FACT-P) and European Quality of Life 5-Dimension-5 Level instruments (EO-5D-5L).

- To evaluate Brief Pain Inventory-Short Form (BPI-SF) with 1st line AAT and 2nd line AAT.
- To evaluate Brief Fatigue Inventory (BFI) with 1st line AAT and 2nd line AAT.
- To determine the benefit of enzalutamide + ADT therapy as compared to flutamide + ADT therapy as assessed by objective response rate (ORR) in soft tissue with 1st line AAT based on the best overall response in Response Evaluation Criteria in Solid Tumors (RECIST) guidelines.
- To evaluate the efficacy in subgroups according to disease-related patient demographics.

3.2 **Study Design**

This is a randomized, open-label, comparative study on enzalutamide and flutamide.

Patients with M0 or M1 castration-resistant prostatic neoplasm that relapsed during combined androgen blockade (CAB) therapy with bicalutamide will be randomized to Group A or B. Dynamic allocation will be performed with minimization with biased coin technique. The following stages (M0/N0, M0/N1, or M1) will be used as allocation factors.

- M0/N0: No distant metastasis, and no lymph node metastasis
- M0/N1: Without distant metastasis, but with metastasis in lymph nodes distal to the aortic bifurcation
- M1: With distant metastasis (including metastasis in lymph nodes proximal to the aortic bifurcation)

For subjects in Group A, enzalutamide is administered as the 1st line AAT. After the confirmation of PSA progression, medication is changed from enzalutamide to flutamide as the 2nd line AAT. For subjects in Group B, flutamide is administered as the 1st line AAT. After the confirmation of PSA progression, medication is changed from flutamide to enzalutamide as the 2nd line AAT. The treatment period with each drug should not be more than 2 years from the enrollment of the last subjects.

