4 SAMPLE SIZE

The number of evaluable subjects will be approximately 200 subjects (1st line AAT enzalutamide group: 100, 1st line AAT flutamide group: 100).

The sample size to evaluate the time to PSA progression with 1st line AAT (TTPP1), which is the primary endpoint of the study, was calculated in consideration of the following points:

• Median TTPP1 with enzalutamide: 10.5 months.

- Median TTPP1 with flutamide: 6 months.
 Values reported in the literature: 5 months according to [Okihara et al., 2007], 6.25 months according to [Narimoto et al., 2010].
- The ratio of randomization of 1st line AAT enzalutamide and flutamide groups is 1:1.

- Subject enrollment period is 12 months, and the observation period is 24 months from the enrollment of the last subject.
- Type I error of the two-sided test is 0.05, and power is 90%.
- A log-rank test with the TTPP1 parameters shown above requires 135 events. The
 necessary number of subjects calculated based on the required number of events is 74
 subjects per group.

Required number of events and necessary number of subjects above are calculated with the formulas below based on [Schoenfeld, 1983]. The codes in the formulas are defined as follows.

 M_t : Median TTPP1 in enzalutamide group

 M_c : Median TTPP1 in flutamide group

 t_a : Enrollment period

 t_f : Observation period from the last subject enrollment

 $Z_{1-\alpha}$: 1- α % point of standard normal distribution

 $Z_{1-\beta}$: 1-β% point of standard normal distribution

Hazard in enzalutamide group $(H_t) = \frac{\log_e 2}{M_t}$

Hazard in flutamide group $(H_c) = \frac{\log_e 2}{M_c}$

Hazard ratio for enzalutamide group/flutamide group (HR) = $\frac{H_t}{H_c}$

Required number of events $(N_d) = \frac{4 \times (Z_{1-\alpha} + Z_{1-\beta})^2}{(\log_e HR)^2}$ *The number after the decimal point will be rounded up to the nearest integer.

Incidence of events of enzalutamide group

$$(P_t) = 1 - \frac{1}{6} \left(\exp\left(-H_t \times t_f\right) + 4 \times \exp\left(-H_t \times \left(t_f + \frac{1}{2} \times t_a\right)\right) + \exp\left(-H_t \times \left(t_f + t_a\right)\right) \right)$$

Incidence of events of flutamide group

$$(P_c) = 1 - \frac{1}{6} \left(\exp(-H_c \times t_f) + 4 \times \exp\left(-H_c \times (t_f + \frac{1}{2} \times t_a)\right) + \exp\left(-H_c \times (t_f + t_a)\right) \right)$$

Incidence of events of both groups $(P) = \frac{1}{2} \times (P_t + P_c)$

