6 ANALYSIS VARIABLES

6.1 Efficacy Endpoints

6.1.1 Primary Efficacy Endpoint(s)

Time to PSA Progression with 1st Line AAT (TTPP1)

PSA progression will be defined according to the consensus guidelines of PCWG2. For patients with PSA declines at Week 13, the PSA progression date is defined as the date that a

 \geq 25% increase and an absolute increase of \geq 2 ng/mL above the nadir is documented, which is confirmed by a second consecutive value obtained 3 or more weeks later. For patients with no PSA decline at Week 13, the PSA progression date is defined as the date that a \geq 25% increase and an absolute increase of \geq 2 ng/mL above the baseline is documented. TTPP1 is defined as the period from the date of randomization to the date of PSA progression in the 1st line AAT period.

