7.4.2.7 Radiographic Progression-Free Survival (rPFS)

The rPFS is defined as the time from randomization to the first objective evidence of radiographic disease progression assessed by the blinded independent central review facility or on-study death, defined as death within 28 days after treatment discontinuation, whichever occurs first. rPFS will be assessed in the ITT population. Radiographic disease progression will include soft tissue disease progression and confirmed bone disease progression. The censoring rules are shown in Table 7-1. The analysis of rPFS will be presented by planned treatment group for subjects that having least one distant metastasis at baseline in ITT population.

rPFS will be assessed using the same method as that with TTPP1. i.e. Stratified log-rank test and unstratified cox regression will be applied to rPFS and estimate the distribution using Kaplan-Meier method.

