7.8 Subgroups of Interest

Primary efficacy endpoint, TTPP2, PSA Response Rate to 1st Line AAT, PSA Response Rate to 1st Line AAT at Week 13 and rPFS, analyses will be repeated by the subgroups defined on the basis of the categorized variables listed below:

- Baseline ECOG performance status (0 vs \geq 1)
- Age category (<75 and ≥ 75 years), (at or below median vs above median)
- Total Gleason score (≤ 7 and ≥ 8) at diagnosis
- Type of progression (PSA progression only vs radiographic progression with or without PSA progression) at study entry
- Baseline PSA value (at or below median vs above median)
- PSA value at initial diagnosis (at or below median vs above median)
- Baseline LDH value (at or below median vs above median)
- Baseline hemoglobin value (at or below median vs above median)
- Baseline ALP value (at or below median vs above median)
- Treatment duration of bicalutamide (at or below 12 months vs above 12 months), (at or below median vs above median)
- PSA nadir value on CAB therapy ($\leq 4 \text{ng/mL vs} > 4 \text{ng/mL}$), ($\leq 0.2 \text{ng/mL vs} > 0.2 \text{ng/mL}$)
- PSA response rate to 1st line AAT at Week 13 (below 50% vs at or above 50% reduction from baseline), (below 90% vs at or above 90% reduction from baseline) *except for the analysis of PSA Response Rate to 1st Line AAT at Week 13.
- Baseline NLR value (at or below median vs above median)
- Baseline testosterone value (at or below median vs above median)
- Treatment duration of first line hormonal therapy (at or below 12 months vs above 12 months), (at or below median vs above median)
- Disease stages (M0/N0 vs M0/N1 vs M1)
- PSA doubling time (at or below median vs above median)

Also, selected safety variables (treatment emergent adverse events) will be summarized by the treatment group for the subgroups defined on the basis of the categorized variables listed below:

- Baseline ECOG performance status (0 vs \geq 1)
- Age category (<75 and ≥ 75 years), (at or below median vs above median)

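### SAP 7.8 compares the arms within strata of Week-13 PSA response, a post-randomization secondary endpoint, so the TTPP1 and rPFS hazard ratios in those rows are not valid treatment-effect estimates

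*SAP*

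**What the plan says.** SAP 7.8 names the primary endpoint, TTPP2, first-line PSA response, Week-13 PSA response "and rPFS, analyses will be repeated by the subgroups defined on the basis of the categorized variables listed below". Nearly all the variables that follow are baseline, diagnosis or pre-study factors. One is not: "PSA response rate to 1st line AAT at Week 13 (below 50% vs at or above 50% reduction from baseline", cut again at 90%. Only the Week-13 response analysis is exempted from this stratifier.

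Protocol 2.3.2 lists the same variable as a secondary endpoint: "PSA response rate to 1st line AAT at Week 13 (decrease by at least 50% or 90% from baseline". SAP 7.4.2.3 compares it between arms. The subgroup objective in SAP 3.1.4 is narrower: "To evaluate the efficacy in subgroups according to disease-related patient demographics".

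The repeated analyses are mostly treatment comparisons. TTPP1 (SAP 7.4.1) gets a stratified log-rank test and an enzalutamide/flutamide hazard ratio. For rPFS (SAP 7.4.2.7), "Stratified log-rank test and unstratified cox regression will be applied to rPFS". Both clocks start at randomization. SAP 7.8 gives no landmark, no rule for subjects without a Week-13 PSA, and no caution about interpretation.

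**The concern.** Randomization makes the arms comparable overall and within strata fixed beforehand. It does not do so within strata that treatment can change. If enzalutamide produces more Week-13 responders, its responders are a less selected group than flutamide's, and its non-responders are a harder residue. Any factor that affects both response and later progression then differs between arms in both strata, and it works against the more active drug. Separately, if part of the benefit acts through early PSA response, conditioning on response removes that part.

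These rows would carry the primary-endpoint hazard ratio in the same subgroup list as valid baseline rows. A drug with the same effect in every patient could appear weaker in both strata than overall, and a reader could take that as evidence about who benefits.

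**Working it through.** **1. The plan's own figures.** The medians are 6 months for flutamide and, in SAP 4, "Median TTPP1 with enzalutamide: 10.5 months". So HR = 6/10.5 = 0.571. Events = 4 × (1.960 + 1.282)² / (ln 0.571)² = 42.03/0.313 = 134.2, rounded up to 135. Event probabilities are 0.858 and 0.966 (mean 0.912), so 0.5 × 135/0.912 = 73.99, i.e. 74 per group. All stated figures reproduce, and none depends on SAP 7.8.

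**2. What is repeated inside the Week-13 strata**

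| Endpoint | Planned analysis | Problem in these strata |
|---|---|---|
| TTPP1 | log-rank, Cox HR | selection; shared sample (step 3) |
| rPFS | log-rank, Cox HR | selection |
| TTPP2 | Kaplan–Meier by group | selection; no test planned |
| First-line PSA response | Mantel–Haenszel test and risk difference | selection; near-circular (step 3) |
| Week-13 response | exempt | none |

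**3. Overlap by definition.** SAP Table 1 schedules no PSA between Day 1 and Week 13. SAP 6.1.1 says "For patients with no PSA decline at Week 13, the PSA progression date is defined as the date" of a sufficient rise above baseline, with no confirmation required. One Week-13 sample can therefore place a subject in the below-50% stratum and also be that subject's TTPP1 event. Conversely, a fall of at least 50% at Week 13 nearly settles first-line PSA50 response, apart from the 3-week condition in SAP 6.1.2. The same holds for PSA90 in the 90% stratum.

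**4. Selection, first model.** From the plan: HR 0.571, flutamide median 6 months, first PSA at Day 85 (85/30.4375 = 2.79 months), and censoring uniform over 24–36 months. Assumed: response 20% (flutamide) versus 60% (enzalutamide); frailty z ~ N(0, s); P(response) = logistic(a − 1.5z), with a set per arm; TTPP1 = 2.79 months plus an exponential time with hazard ln 2/(6 − 2.79) × exp(z) × HR. There are 400,000 subjects per arm, and each subject has the same conditional HR, set so that the overall HR is 0.571.

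| s | Conditional HR | Overall | Responders | Non-responders |
|---|---|---|---|---|
| 0 | 0.572 | 0.57 | 0.57 | 0.57 |
| 0.5 | 0.516 | 0.57 | 0.63 | 0.64 |
| 0.8 | 0.465 | 0.57 | 0.71 | 0.71 |
| 1.0 | 0.426 | 0.57 | 0.76 | 0.75 |

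Other settings, with s from 0.5 to 1.0:
- **No drug effect, 50% cut:** overall 1.00, strata 1.12–1.40.
- **No drug effect, 90% cut (assumed 5% versus 30%):** 1.11–1.44 at or above the cut, 1.08–1.22 below it.
- **Stage-stratified Cox (stage assumed to carry 30% of frailty variance, same conditional HRs):** overall 0.54–0.56, strata 0.60–0.68. With no drug effect, strata 1.09–1.32.
- **Weaker prognosis–response slope (unadjusted):** slope 0.75 gives strata of 0.61–0.68 (no effect 1.07–1.21); slope 0.4 gives 0.58–0.63 (no effect 1.04–1.11).

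**5. Selection, second model.** This has no lead-in. Response follows a probit model with correlation 0.6 to prognosis, log-HR is 0.5 or 1.0 per SD, and response rates are 70/35%, 60/20% or 80/40% (enzalutamide/flutamide).
- **No effect (overall 0.99–1.02):** responders 1.16–1.39, non-responders 1.17–1.40.
- **Planned effect (overall 0.56–0.58):** responders 0.65–0.75, non-responders 0.66–0.78.
- **Equal response (50/50%):** strata agree with overall to within about 0.03, so the distortion comes from the arm difference in the stratifier.

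**6. Mediation.** Suppose the drug acts only through Week-13 response (responder hazard 0.2–0.4 times that of non-responders; response rates as in step 5 plus 80/20%). The overall HR is then 0.45–0.76, but both strata show 0.97–1.03.

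**7. Balance.** At 100 per arm, the step 5 rates (excluding 50/50%) give responder strata of 60–80 versus 20–40 subjects, and non-responder strata of 20–40 versus 60–80.

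**The case against.** The best counter-argument accepts the structure and attacks the size. The range 0.63–0.76 rests on a prognosis–response slope of 1.5 that nothing in the documents supports, and gentler slopes shrink it, as step 4 shows. The first model also does not reproduce the planned medians. With the 85-day lead-in and HR 0.57, enzalutamide medians come out at 8.4–9.7 months rather than 10.5. With zero frailty, reaching 10.5 would need a post-lead-in HR of about 3.21/7.71 = 0.42. The headline is unadjusted, whereas SAP 7.4.1 adjusts for stage as a covariate, and the stage-stratified run was not recalibrated to 0.57. No model quantifies the shared-sample overlap in step 3.

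These points stand as limits on the numbers. They do not reverse the direction. The weaker-slope results lie between no distortion and 0.76, and the second model, which has no lead-in, gives similar values.

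The remaining objections concern consequence. Subgroup efficacy is exploratory, Protocol 7.4.1.3 leaves subgroup choice to the SAP, and the objective's reference to demographics is loose wording. Table layouts are in specifications not available here, so a caution might appear there. These points fairly limit the importance. But nothing in the SAP supplies the caution, and exploratory status does not turn a non-randomized contrast into a treatment effect.

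**Conclusion.** The concern holds. Followed as written, SAP 7.8 produces between-arm hazard ratios and tests within strata that treatment itself can change, and exempts only one of the five endpoints. They would be undistorted only if no prognostic factor influenced both Week-13 response and progression and no part of the drug's effect ran through that response. The plan does not argue for either condition.

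The direction is towards making the more responsive arm look worse in both strata. Under the assumptions above, an overall HR of 0.57 becomes anything from about 0.57 to 0.78 within strata, and no effect becomes anything from 1.0 to about 1.4. If the benefit is fully mediated, it disappears within strata. These are illustrations, not predictions.

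The consequence is confined to interpreting exploratory rows. The ITT stratified log-rank test, 135 events, 74 and 100 per group, and the baseline subgroups are untouched. This should be fixed, but it does not threaten the trial's main conclusion.

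**What to change.** Delete the Week-13 PSA response bullet, both cuts, from the treatment-comparison subgroups in SAP 7.8, and keep the baseline factors.

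If the link between early response and later outcome is of interest, replace the bullet with a landmark description:
- Start the clock at Week 13 and include only subjects still on the first drug and progression-free.
- Compare responders with non-responders within each arm.
- Label the result descriptive and non-causal, with no between-arm hazard ratio or test.
- Do not apply it to the PSA-response endpoint.

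A landmark alone is not enough if the arms are still compared. It deals with time before Week 13 but leaves the selection between arms.

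Deletion costs one bullet and removes tables. The landmark option needs a new risk set and a few tables, but no new data. SAP version 1.00 is marked final, so the change needs a SAP revision or, under SAP 1, a justification in the clinical study report.

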The treatment-emergent period will be defined as the period of time from the date of the first dose of study drug to 28 days after the date of the last dose of study drug, or 1 day prior to the date of initiation of cytotoxic chemotherapy for prostate cancer or an investigational agent treating prostate cancer, whichever occurs first. And 1st line treatment-emergent period is defined as the period of time from the date of the first dose of study drug in 1st line to 28 days after the date of the last dose of study drug in 1st line, or 1 day prior to the date of initiation of cytotoxic chemotherapy for prostate cancer or an investigational agent treating prostate cancer, whichever occurs first. Regarding 2nd line treatment-emergent period is applied same rule for 2nd line date.

• Baseline Value and Post-Baseline Value

Unless otherwise specified, the baseline value is defined as the last non-missing measurement prior to the randomization of study drug. When analysis be provided separately by treatment lines, baseline value for 2nd line AAT is defined as the last non-missing value measurement prior to the enrollment for 2nd line AAT of study drug.

Post-baseline value is defined as a measurement taken after the randomization of study drug. For Post-baseline value for 2nd line is defined as a measurement taken after enrollment during of study for 2nd line AAT.

Baseline value is defined as the last non-missing measurement prior to randomization (or register of 2nd line AAT) and post-baseline value is defined as a measurement taken after randomization for subjects who did not receive study drug. Change from baseline is defined as (post-baseline value - baseline value). Both date and time of drug administration and measurement should be considered when calculating baseline value. If time is not available, then date only should be used.

Treatment Group

Treatment group is defined as planned randomized treatment sequence which divide to initial enzalutamide 160 mg/day group or the initial flutamide 125 mg × 3 times daily (375 mg/day) group.

• Treatment Arm

Treatment arm is defined as administration drug group regardless 1st line or 2nd line treatment. That is enzalutamide plus ADT arm include subject who receive enzalutamide plus ADT at 1st line and 2nd line. Flutamide plus ADT include who receive flutamide plus ADT at 1st line and 2nd line.

• Treatment Line

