All analysis of safety will be presented by actual treatment group for SAF, unless specified otherwise. The last non-missing measurement prior to the first dose of study drug will be used as the baseline.

7.5.1 **Adverse Events**

The severity of all AEs is to be evaluated by the investigator based on the National Cancer Institute's CTCAE version 4.0. The coding dictionary for this study will be Medical Dictionary for Regulatory Activities (MedDRA) version 19.1. It will be used to summarize AEs by SOC and PT.

The safety analysis will be performed in the safety analysis set, and summarized by the time of assessment and by the treatment group that actually received the study drugs. The period of onset in the treatment period with the study drug is defined up to 28 days after the final treatment with the study drug, start date of cytocidal chemotherapy, or start date of new treatment for prostate cancer, whichever occurs first. Safety will be assessed by AEs, frequency of treatment discontinuation associated with AEs, and laboratory test value summary statistics. Descriptive statistics, and not inferential statistics, will be used.

The total number of AEs reported will be presented by treatment arm (i.e. enzalutamide v.s. flutamide) and overall total for the SAF. The same analysis will be provided dividing treatment lines. AEs which have occurred during 1st line AAT and 2nd line AAT will be included to analysis. In this 'event level' analyses, all AEs will be counted separately. The following categories will be presented:

- Number of AEs,
- Number of AEs leading to study drug discontinuation,
- Number of drug-related AEs,
- Number of drug-related AEs leading to study drug discontinuation,
- Number of grade 3 or higher AEs,
- Number of grade 3 or higher drug-related AEs,
- Number of serious adverse events (SAEs),

- Number of drug-related SAEs,
- Number of SAEs leading to study drug discontinuation,
- Number of drug-related SAEs leading to study drug discontinuation,
- Number of SAEs leading to death,
- Number of drug-related SAEs leading to death.

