The number and percentage of subjects experiencing AEs will be presented by treatment arm and overall total for the SAF. The same analysis will be provided dividing treatment lines. AEs which have occurred during 1st line AAT and 2nd line AAT will be included to analysis. In this 'subject level' analyses, multiple AEs within the same category for a particular subject will only be counted once and the denominator for the percentage calculation will be the number of subjects in the SAF. The following categories will be presented:

- Number and percentage of subjects with AEs,
- Number and percentage of subjects with AEs leading to study drug discontinuation,
- Number and percentage of subjects with drug-related AEs,
- Number and percentage of subjects with drug-related AEs leading to study drug discontinuation,
- Number and percentage of subjects with grade 3 or higher AEs,
- Number of grade 3 or higher drug-related AEs,
- Number and percentage of subjects with SAEs,
- Number and percentage of subjects with drug-related SAEs,
- Number and percentage of subjects with SAEs leading to study drug discontinuation,
- Number and percentage of subjects with drug-related SAEs leading to study drug discontinuation,
- Number and percentage of subjects with SAEs leading to death,
- Number and percentage of subjects with drug-related SAEs leading to death.

The number and percentage of subjects experiencing AEs will be tabulated by SOC, PT, treatment arm and overall total for the SAF. The same analysis will be provided dividing treatment lines. AEs which have occurred during 1st line AAT and 2nd line AAT will be included to analysis. For this and similar analyses, an AE will only be counted once for each subject if the same AE is experienced on more than one occasion. Tables will be sorted by descending overall total of SOC and PT frequency. The following summaries will be produced:

- AEs,
- AEs leading to study drug discontinuation,
- drug-related AEs,
- drug-related AEs leading to study drug discontinuation,
- grade 3 or higher AEs,
- SAEs,

- drug-related SAEs,
- SAEs leading to study drug discontinuation,
- drug-related SAEs leading to study drug discontinuation,
- SAEs leading to death,
- drug-related SAEs leading to death,
- TEAEs excluding serious adverse events that equal to or exceed a threshold of 2.0% in any treatment group, and
- Common TEAEs that equal to or exceed a threshold of 2.0% in any treatment group.

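### SAP 7.8 tabulates subgroup adverse events by treatment group (the randomized sequence), while SAP 6.2, 7.1.1, 7.5 and 7.5.1 point to the drug taken; the wording should be aligned

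*SAP*

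**What the plan says.** SAP 7.1.2 defines two terms. On the first: "Treatment group is defined as planned randomized treatment sequence", that is, initial enzalutamide or initial flutamide. On the second: "Treatment arm is defined as administration drug group regardless 1st line or 2nd line treatment".

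The main adverse event tables in SAP 7.5.1 use the second term. At event level: "The total number of AEs reported will be presented by treatment arm (i.e. enzalutamide v.s. flutamide) and overall total for the SAF". At subject level: "The number and percentage of subjects experiencing AEs will be presented by treatment arm and overall total for the SAF". Each set is then split: "The same analysis will be provided dividing treatment lines". Both lines are covered: "AEs which have occurred during 1st line AAT and 2nd line AAT will be included to analysis".

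For the subgroups by baseline ECOG status (0 versus 1 or more) and age (below 75 versus 75 or more, and a median split), SAP 7.8 uses the first term: "selected safety variables (treatment emergent adverse events) will be summarized by the treatment group for the subgroups". It gives no split by line, no restriction to 1st line and no denominator.

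Three other places bear on the reading. SAP 6.2 assigns each event to a treatment arm through the treatment-emergent period. SAP 7.1.1 presents summaries on the safety set by the treatment actually received. SAP 7.5 makes the actual treatment group the safety default unless something else is specified.

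**The concern.** Switching to the other drug is the planned course after PSA progression. The overall treatment-emergent period in SAP 7.1.2 starts at the first dose of either drug. It ends 28 days after the last dose, or the day before chemotherapy or an investigational agent if that is earlier. It therefore spans both lines. Under the defined meaning of *treatment group*, a 2nd-line flutamide event falls in the initial-enzalutamide column, and a 2nd-line enzalutamide event in the initial-flutamide column.

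The safety objective (SAP 3.1.3) compares one drug with the other, and the 7.8 tables are the only planned adverse event tables by age or ECOG status. Tabulated by sequence, they would understate any difference in tolerability between the drugs in older or less fit patients. They would also use a different unit from the 7.5.1 tables beside which they will be read.

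**Working it through.** **1. How common switching would be.** The documents give no switching rate, but the sample size section (SAP 4, protocol 7.1) gives the parts. Its own figures reproduce:

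- Hazard ratio = 6 / 10.5 = 0.571.
- Events = 4 × (1.960 + 1.282)² / (ln 0.571)² = 134.2, rounded up to 135, as stated.
- The SAP incidence formula with 12 months of accrual and 24 months of follow-up gives 0.858 (enzalutamide first) and 0.966 (flutamide first), mean 0.912.
- Subjects per group = 0.5 × 135 / 0.912 = 73.99, rounded up to 74, as stated.

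On the design assumptions, then, 86% and 97% would reach 1st-line PSA progression and be due to switch. If 25% in each group never switch (an assumption, set equal to the plan's dropout allowance), the shares are 0.75 × 0.858 = 0.644 and 0.75 × 0.966 = 0.725.

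**2. Dilution under the literal reading.** Let pE and pF be the risks of an event while on enzalutamide and on flutamide. Assume the same risk in either line, independence between lines and the same switching share s in both sequences.

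- Enzalutamide first: A = 1 − (1 − pE)(1 − s·pF) = pE + s·pF − s·pE·pF
- Flutamide first: B = 1 − (1 − pF)(1 − s·pE) = pF + s·pE − s·pE·pF
- Difference: B − A = (1 − s)(pF − pE)

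The fraction left is (1 − s), whatever the two risks are.

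**3. Illustration.** Flutamide AST increase is 13.2% (protocol 1.4.2) and enzalutamide fatigue is 25.3% (protocol 1.4.1). The rate on the other drug is set at 1% in each case; that is an assumption, not a figure from the documents.

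| s (assumed) | Fraction left | AST: true 12.2 points | Fatigue: true 24.3 points |
|---|---|---|---|
| 0.60 | 0.40 | 4.88 | 9.72 |
| 0.75 | 0.25 | 3.05 | 6.08 |
| 0.90 | 0.10 | 1.22 | 2.43 |

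With the unequal shares from step 1:

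- AST: A = 1 − 0.99 × (1 − 0.644 × 0.132) = 9.4%; B = 1 − 0.868 × (1 − 0.725 × 0.01) = 13.8%. The difference is 4.4 points, about 36% of 12.2.
- Fatigue: A = 1 − 0.747 × (1 − 0.644 × 0.01) = 25.8%; B = 1 − 0.99 × (1 − 0.725 × 0.253) = 19.2%. The difference is 6.6 points, about 27% of 24.3.

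**4. A gauge without event rates.** Times were simulated as exponential, with follow-up uniform from 24 to 36 months, each drug's 2nd-line hazard 1 to 2 times its 1st-line hazard, and 0 to 25% never switching. The second drug then takes about 17–32% of on-treatment time in the enzalutamide-first group and 37–56% in the flutamide-first group.

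**The case against.** The strongest reply is that the mixing is only one reading. SAP 6.2 gives a route for a switcher's events: each is assigned to an arm through the treatment-emergent period, with a fallback for missing dates and a rule against carrying a continuing 1st-line event into 2nd line. SAP 7.1.2 also defines separate 1st-line and 2nd-line treatment-emergent periods. SAP 7.1.1 and 7.5 set actual treatment as the safety default.

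The vocabulary is loose as well. SAP 7.5.1 speaks of the treatment group that actually received the drugs, and applies a 2.0% threshold per treatment group inside tables organized by arm. SAP 7.2.4 uses treatment arm for medication taken before any study drug. SAP 7.2.2, 7.2.5 and 7.2.6 add *as randomized* after treatment group, which the definition would make redundant. Careless terminology is a plausible explanation.

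That stands as far as it goes: it shows an internal conflict, and it rules out saying that the tables will certainly mix drugs. It does not cure 7.8. The default in 7.5 yields where something else is specified, and 7.8 specifies a defined term. The actual treatment group is not itself defined, and a switcher has two actual treatments. None of these places supplies the missing line split or denominator.

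The size is also fairly challenged. The 1% rates are assumed. The 13.2% comes from a pool of adverse reactions and abnormal laboratory values, not trial events. Equal risk in both lines is doubtful for AST, because protocol 3.4 bars a move to 2nd-line flutamide when the latest AST or ALT is above normal; that selection would probably lessen the dilution.

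**Conclusion.** The conflict is real and worth correcting. Under the defined term, 7.8 tabulates by sequence, against the approach in SAP 6.2, 7.1.1, 7.5 and 7.5.1. The loss on that reading is a fraction, (1 − s) retained, and rests on equal switching, equal per-drug risk in both lines and independence between lines. With the unequal shares derived from the design figures, roughly a quarter to a little over a third of the contrast remains in the two examples.

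A reader might infer three stronger things that the documents do not support:

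- **The subgroup tables are bound to mix the two drugs.** The counter-text leaves that open.
- **The percentage-point figures are forecasts.** They are illustrations on assumed rates.
- **The subgroup tables could not be reconciled with the main ones.** Both come from the same safety set and the same event records, so a retabulation would reconcile them.

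The consequence is confined to descriptive safety tables. No test, alpha, sample size or efficacy result changes.

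**What to change.** In SAP 7.8, replace *by the treatment group* with *by treatment arm, and again by treatment line*, as in 7.5.1. State the denominators: subjects of the subgroup who received that drug, and for the line split, who received it in that line. They need to be spelled out, because 7.5.1 says only that percentages use the number of subjects in the safety set.

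Check the same term in SAP 7.5.2 and 7.5.3. By-visit summaries may need no change if visits are numbered within line, since group and visit then identify the drug. The counts of grade 3 or 4 laboratory values and the low/normal/high shift table are per treatment group with no line split stated, so the intended grouping should be made explicit there. The liver test tables in 7.5.2.1 and the ECOG tables in 7.5.4 already use arm and line.

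The cost is one phrase in 7.8 plus this check. The groupings are already required for 7.5.1, and no new data are needed. If the SAP can no longer be changed, record the grouping used and the reason in the clinical study report, as SAP 1 provides.
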